### 12.3.1.3. Binary Endpoints

For binary endpoints, number (%) of subjects and its 95% CI derived from the normal approximation to the binomial will be summarized based on ITT by designated treatment site and pooled designated treatment site. The denominator for a treatment site is determined by numbers of subjects with the designated site. The number and percent of missing data will be shown.

The missing data of binary endpoints will not be imputed for exploratory endpoints.

### 12.3.1.4. Exploratory Endpoints

For continuous and binary exploratory endpoints, the analyses will be the same as ones in Section 12.3.1.2 and Section 12.3.1.3. For the time-to-event efficacy endpoint, the Kaplan-Meier curves will be presented based on the ITT population. Subjects not having any event during the study will have their time censored at the last available date in the study. The Kaplan-Meier estimates and 95% CIs for the 25th percentile, 50th percentile and 75th percentile will be presented.

For each exploratory continuous endpoint, the summary statistics with 95% confidence interval (CI) will be presented based on the ITT population by designated treatment site and pooled designated treatment site.

The exploratory endpoints for this study are:

- Mean percent area of StrataGraft treatment site closed without autograft placement at Week 8
- Mean Patient and Observer Scar Assessment Scale (POSAS) observer total score at Week 12, and Months 6 and 12.
- Changes in skin quality outcome (POSAS and Patient Scar Assessment Questionnaire [PSAQ] scores) across time.
- Incidence and severity of pain at the treatment site using EVENDOL (EValuation ENfant DOuLeur, ie, Evaluation of Child Pain; observer or parent) or FPRS (Wong-Baker Faces Pain Rating Scale with 6 faces with expressions denoting degrees of pain; subject) over time.
- Percent of subjects with complete closure of StrataGraft treatment site without autografting at Weeks 6 and 8 and Months 6 and 12.
- Time to complete closure following application of StrataGraft.
- Mean percent wound closure over time from Day 21 through Month 12.
- Percent of subjects achieving and maintaining persistent wound closure at Months 6 and 12.
- Mean scar satisfaction based on PSAQ scores at Week 12 and Months 6 and 12.

**Table 7: The Objective, Population, Hypothesis, Endpoint and Intercurrent Events and Data Handling for the Primary Endpoint**

Objective	Population	Hypothesis	Endpoint	Intercurrent Events and Data Handling
To evaluate whether StrataGraft treatment eliminates or reduces the need for autografting and promotes wound closure in a pediatric population with thermal burns that contain intact dermal elements and for which autografting is clinically indicated.	All enrolled subjects who received StrataGraft	$H_0$ : The response rate of primary endpoint is less than or equal to the 50% $H_1$ : The response rate of the primary endpoint is greater than the 50%  Positive study criteria: The lower bound of primary endpoint 95% CI derived from the normal approximation to the binomial $> 50\%$ .	Percentage of subjects achieving confirmed complete closure of all StrataGraft treatment sites on or before Week 12 without autograft placement. Confirmed complete wound closure is defined as 100% re-epithelialization confirmed at 2 visits at least 2 weeks apart but before Week 20.	Early discontinuation due to: 
 
• Withdrawal of informed consent
 
• Lost to follow-up
 
• Adverse event
 
• Investigator decision
 
• Death
 
• Other
 
 Missing/incomplete data will be imputed as failure (ie, no confirmed complete wound closure).

CI = Confidence Interval; LB = Lower Bound

**Table 8: The Objective, Population, Hypotheses, Endpoints and Intercurrent Events and Data Handling for Ranked Secondary Efficacy Endpoints**

Objectives	Population	Hypotheses	Endpoints	Intercurrent events and data handling
To evaluate the mean averaged percent of wound area closure of StrataGraft treatment site without autograft placement at Week 12	All enrolled subjects who received StrataGraft	$H_{01}$ : Mean of averaged percent wound area closure of StrataGraft treatment site without autograft placement at Week 12 $\leq 50\%$ $H_{11}$ : Mean percent of wound area closure of StrataGraft treatment site without autograft placement at Week 12 $> 50\%$	Mean of averaged percent area of StrataGraft treatment site closed without autograft placement at Week 12	
Early discontinuation due to:
 
 
• Withdrawal of informed consent
 
• Lost to follow-up
 
• Adverse event
 
• Investigator decision
 
• Death
 
• Other
 
 
Missing/incomplete continuous variables will not be imputed.

To evaluate the number (%) of StrataGraft treatment sites with confirmed complete wound closure without autograft placement on or before Week 12	All enrolled subjects who received StrataGraft	$H_{02}$ : The response rate of StrataGraft treatment sites with confirmed complete wound closure without autograft placement on or before Week 12 is less than or equal to the 50% $H_{12}$ : The response rate of StrataGraft treatment Sites with confirmed complete wound closure without autograft placement on or before Week 12 is greater than the 50%	Number (%) of StrataGraft treatment sites with confirmed complete wound closure without autograft placement on or before Week 12	
Missing/incomplete binary variable will be imputed as failure.

Objectives	Population	Hypotheses	Endpoints	Intercurrent events and data handling
To evaluate the mean averaged percent area of StrataGraft treatment sites autografted per subject by Week 12	All enrolled subjects who received StrataGraft	$H_{02}$ : Mean of averaged percent area of StrataGraft treatment sites autografted per subject by Week 12 $>50\%$ . $H_{12}$ : Mean of averaged percent area of StrataGraft treatment sites autografted per subject by Week 12 $<50\%$ .	Mean of averaged percent area of StrataGraft treatment sites per subject autografted by Week 12	

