**Table 1: Abbreviations and Specialist Terms**

Abbreviation	Explanation
AE	Adverse event
AESI	Adverse Event of Special Interest
BSA	Bovine serum albumin
CBC	Complete blood count
CFR	Code of Federal Regulations
CI	Confidence Interval
CMP	Comprehensive metabolic panel
Complete closure	Complete re-epithelialization without drainage
Confirmed complete closure	Complete wound closure confirmed at 2 consecutive visits at least 2 weeks apart but no later than Week 20
DPT	Deep partial thickness, defined as a wound extending into the dermis but that contains intact dermal elements and for which excision/debridement and autografting are clinically indicated
DMC	Data Monitoring Committee
eCRF	Electronic case report form
EVENDOL	EValuation ENfant DOuLeur, ie, Evaluation of Child Pain, a validated scale used to measure pain in pre-verbal children by assessing behavioral cues
FPRS	Wong–Baker Faces Pain Rating Scale, a validated scale of 6 faces with expressions denoting degrees of pain
FDA	US Food and Drug Administration
GCP	Good Clinical Practice
HIPAA	Health Insurance Portability and Accountability Act
ICC	Intraclass correlation coefficient
ICF	Informed consent form
ICH	International Council for Harmonisation
IEC	Independent Ethics Committee
IP	Investigational Product
IRB	Institutional review board
ITT	Intent-to-treat
LB	Lower Bound
Persistence of Closure	Maintenance of wound closure for at least 3 months after confirmation of complete wound closure.
POSAS	Patient and observer scar assessment scale
PRA	Panel reactive antibodies

[figure not shown]
PSAQ	Patient Scar Assessment Questionnaire
SAE	Serious adverse event
SAP	Statistical Analysis Plan
StrataSTEPS	StrataGraft Safety, Tolerability and Efficacy in Pediatric Subjects
TBSA	Total body surface area
TEAE	Treatment emergent adverse event

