### 12.3.1.2. Ranked Secondary Endpoints

After the primary endpoint is successfully reached, the ranked secondary efficacy endpoints will each be tested with a 2-sided confidence interval with 0.05 Type I error in a hierarchical manner in the rank order as in [Table 8](#). The ranked secondary endpoints are:

1. Mean of averaged percent area of StrataGraft treatment site closed per subject at Week 12 without autograft placement
2. Number (%) of confirmed complete wound closures of the StrataGraft treatment sites on or before Week 12 without autograft placement
3. Mean of averaged percent area of StrataGraft treatment site autografted by Week 12

For continuous efficacy endpoints, missing data will not be imputed. Missing or incomplete binary variables will be imputed as failures. Missing data are anticipated to occur only if the subject is lost to follow-up because information can be obtained for a missing visit when the subject returns for a subsequent visit. If a subject has autograft placement, the data collected after the autograft placement will be censored.

The averaged percent area closed per subject at Week 12 will be calculated as (Sum of percent area closed across treatment sites for a subject at Week 12/the total number of treatment sites on a subject).

The percentage of StrataGraft treatment sites with confirmed complete wound closure on or before Week 12 will be calculated as [(Total number of StrataGraft treatment sites with confirmed complete wound closure without autografting on or before Week 12/Total number of treatment sites) x 100].

The averaged percent area of StrataGraft treatment sites per subject autografted by Week 12 will be calculated as (Sum of percent area of StrataGraft treatment sites per subject autografted by Week 12/the number of treatment sites on that subject). It is a cumulative sum of percent area autografted for all nonmissing visits on or before Week 12.

The summary statistics with 95% confidence interval (CI) and p-value based on null hypothesis specified in [Table 8](#) for each endpoint from t-distribution will be presented based on the ITT population by designated treatment site and pooled designated treatment site. The analyses by age cohort will be presented.

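### The exploratory persistent-closure endpoint has no autograft condition, and the plan's rules conflict on how an autografted child counts

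*Combined protocol and SAP*

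**What the plan says.** The persistence endpoint appears in the Synopsis, Section 5.3 and Section 12.3.1.4 as "Percent of subjects achieving and maintaining persistent wound closure at Months 6 and 12". Table 1 defines persistence as "Maintenance of wound closure for at least 3 months after confirmation of complete wound closure" and the confirmed closure on which it builds as "Complete wound closure confirmed at 2 consecutive visits at least 2 weeks apart but no later than Week 20". Neither definition mentions autograft, and nor does the Table 1 entry for complete closure.

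Other closure endpoints do carry the condition. The primary endpoint and the first two ranked secondary endpoints are limited to closure without autograft. So is the neighbouring item in the 12.3.1.4 list, "Percent of subjects with complete closure of StrataGraft treatment site without autografting at Weeks 6 and 8 and Months 6 and 12", which covers the same two late time points.

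Four rules bear on an autografted child:

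- Section 12.3.1.2, on the ranked secondary endpoints: "If a subject has autograft placement, the data collected after the autograft placement will be censored".
- Section 12.3.1.4 extends the earlier sections: "For continuous and binary exploratory endpoints, the analyses will be the same as ones in Section 12.3.1.2 and Section 12.3.1.3".
- Section 12.3.1.2 and the Synopsis treat a missing binary result as a failure.
- Section 12.3.1.3: "The missing data of binary endpoints will not be imputed for exploratory endpoints". The same section sets the denominator for a treatment site by the subjects who have that site, and has missing data displayed separately.

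**The concern.** The trial's objective is to find out whether StrataGraft removes or reduces the need for autografting. A child whose treatment site had to be autografted fails the primary endpoint. Under the literal persistence definition the same child can be a success at Months 6 and 12, so the durability of the autograft is credited to StrataGraft. Because the adjacent endpoint states the condition and this one does not, a programmer or reader could take the omission as deliberate.

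The rules elsewhere in Section 12 do not settle the matter. Depending on which sentence is followed, the same child is a success, is left out, or is a non-success, and the reported percentage differs accordingly.

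Time to complete closure has a related gap. Its only stated censoring rule covers children with no event, and the carry-over sentence in 12.3.1.4 names continuous and binary endpoints only. Closure after an autograft could therefore be counted as a StrataGraft closure event.

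**Working it through.** **The plan's own figure.** The documents give no expected rate for persistence. The only related figure is the power of the primary endpoint in Section 12.1 (above 90% with 50 children, true rate 83%, lower 95% limit set against 50%). It reproduces: with the normal-approximation interval, 32 of 50 responders are needed and exact binomial power is 0.9997; with 40 children, 26 are needed and power is 0.998. The persistence endpoint does not affect this calculation.

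**Can an autografted child meet the definition?** Table 2 and Section 10.4 schedule closure assessment through Month 12, and no text stops it at autografting. Table 2 keeps photographs at Months 6 and 12 after an autograft, and Section 11.9.2 foresees autograft as a way to speed closure. Take a site autografted at Week 3, first seen closed at Week 5, confirmed at Week 7 and intact at Month 6. Confirmation falls before Week 20. Three months after it is about Week 7 + 13 = Week 20, and Month 6 is about Week 26. The definition is met as written.

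**Possible scorings of that child.**

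1. Success: the endpoint and Table 1 are applied as worded, with no censoring.
2. Dropped: post-autograft data are censored under 12.3.1.2, the missing value is not imputed under 12.3.1.3, and the denominator is taken as observed children.
3. Non-success: data are censored, and then either the missing value becomes a failure (12.3.1.2 and Synopsis) or it is not imputed but the child stays in the 12.3.1.3 denominator.

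Section 12.3.3 adds to the conflict: it says missing data for the ranked secondary endpoints are not imputed, against the failure rule for binary variables in 12.3.1.2.

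**Size.** All counts here are assumptions. Let N = 50, let 4 children fail for reasons unrelated to autograft, and let *a* be the children autografted whose wounds then close and stay closed. Children persistent without a graft number s = 50 − 4 − a.

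- Success: (s + a)/50
- Dropped: s/(50 − a)
- Non-success: s/50

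| a | s | Success | Dropped | Non-success |
|---|---|---|---|---|
| 2 | 44 | 46/50 = 92.0% | 44/48 = 91.7% | 44/50 = 88.0% |
| 5 | 41 | 46/50 = 92.0% | 41/45 = 91.1% | 41/50 = 82.0% |
| 8 | 38 | 46/50 = 92.0% | 38/42 = 90.5% | 38/50 = 76.0% |

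Success exceeds non-success by a/50: 4, 10 and 16 points. Dropping the child gives nearly the same figure as counting a success; it exceeds non-success by 3.7, 9.1 and 14.5 points.

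**Which row is plausible?** Section 6.2 reports that more than 95% of adult subjects closed without autografting. If children behaved the same way, fewer than 5% of 50, or at most 2, could be autografted and healed. That is the first row. The documents give no paediatric rate.

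**The case against.** The strongest reply is that little depends on this endpoint. It is exploratory, with no hypothesis, no success criterion and no place in the ranked hierarchy. The same list already reports "Percent of subjects with complete closure of StrataGraft treatment site without autografting" at Months 6 and 12, so an autograft-free late result would stand beside it. The SAP memo states that, with one subject enrolled, there will be no formal analyses. Listings 16.2.5.6 and 16.2.6.2 would show any additional autograft and the closure assessments directly. All of this stands and limits the importance of the point.

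Three stronger readings are tempting, and the documents do not support them.

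- A reader might infer that an autografted child can never count as a failure. The failure imputation in 12.3.1.2 and the Synopsis, or the denominator in 12.3.1.3, can make the child a non-success. The exploratory no-imputation sentence is the more specific rule and probably prevails over imputation, but it does not say that the child leaves the denominator. An autografted child whose closure is not confirmed by Week 20, or not maintained, also fails the definition.
- A reader might infer that this is the only durability result after Week 20. Autograft-free closure at Months 6 and 12 and mean percent closure through Month 12 are also listed. It is only the one endpoint that uses the defined term for persistence.
- A reader might infer an excess of up to 17 points from the planning rate (100 − 83). That is a ceiling, not an expectation. Section 4.2 says the adult 83% counted missing data as failures, so the shortfall is not all autografted and healed wounds.

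**Conclusion.** The point holds as a minor one. The persistence endpoint and its Table 1 definitions lack the autograft condition found in the primary endpoint and in the neighbouring Month 6 and 12 endpoint. As written, an autografted and healed child can be a persistent success, which runs against the trial's objective. If post-autograft censoring is carried over, the conflicting rules allow the child to be dropped or scored as a non-success, and no text chooses between them.

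The illustrative excess over non-success handling is about 4 points with 2 such children and up to 16 points with 8. The adult figure in Section 6.2 points to the low end. These sizes rest on the assumed counts and on adult experience applying to children. No power, test or success criterion changes, and under the SAP memo no rate will be computed. The defect matters for the protocol text and for any reuse of it.

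**What to change.** In the Synopsis, Section 5.3 and Section 12.3.1.4, reword the endpoint to persistent wound closure without autograft placement at Months 6 and 12. State that a child autografted on any treatment site stays in the denominator and counts as not persistent at both times. This removes the dependence on the censoring, imputation and denominator rules for such children.

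Apply the same condition to time to complete closure, so that closure after an autograft is not counted as a StrataGraft closure event.

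The cost is a few words in three places and one sentence on scoring. The reported persistence rate would be slightly lower than under the literal wording. No additional data are needed, since the area autografted and wound closure are already collected.

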### **12.3.2. Safety Analyses**

All subjects who receive StrataGraft treatment will be included in the safety analyses.

AEs will be coded using the Medical Dictionary for Regulatory Activities coding classifications and presented by preferred term within system organ class. The number of AEs and the number of subjects reporting AEs will be listed and summarized descriptively by body system, preferred term, severity, and causality by designed StrataGraft (SG) treatment site, and pooled SG designated treatment sites, non-SG burn site, donor site, another site and pooled for all sites. All SAEs will be summarized and narratives will be created as appropriate.

### **12.3.3. Handling of Missing Data**

Subjects will be encouraged to return to clinic for each scheduled visit. Direct observation of the wound and collection of data at scheduled times is essential to ensure the quality of the data. However, should a visit be missed, thereby resulting in missing data for that visit, the following approaches will be employed to manage the missing data.

For the primary efficacy endpoint, missing/incomplete data will be imputed as failure (ie, no confirmed complete wound closure).

For the ranked secondary endpoints, missing/incomplete data will not be imputed.

A full description of missing data imputation methods for all endpoints will be described in detail in the SAP.

## **13. SUPPORTING DOCUMENTATION AND OPERATIONAL CONSIDERATIONS**

The study will be conducted in full compliance with applicable international, national, and local regulatory requirements, including US Food and Drug Administration (FDA) regulations, 21 Code of Federal Regulations (CFR) Parts 56, 314.106 and 312.120 (where applicable), International Council on Harmonization (ICH) guidelines for Good Clinical Practice (GCP) in accordance with the ethical principles that have their origins in the Declaration of Helsinki, and European regulation 536/2014/EU (where applicable).

### **13.1. Institutional Review Board (IRB)**

It is the responsibility of the investigator to obtain the approval of the IRB/independent ethics committee (IEC) before the start of the study. A copy of the approval letter along with a roster of IRB/IEC members and compliance letter or their US Department of Health and Human Services general assurance number will be provided to the Sponsor and retained as part of the study records. During the course of the study, the investigator will provide timely and accurate reports to the IRB/IEC on the progress of the study at appropriate intervals and at the completion of the study. The investigator will notify the IRB/IEC of SAEs or other significant safety findings per IRB/IEC guidelines. The study protocol, ICF, advertisements (if any), subject-facing materials, and amendments (if any) will be approved by the IRB/IEC in conformance with international, national, and local regulatory requirements.

An investigator may not make any changes in the conduct of the study without IRB/IEC and Sponsor approval except when necessary to eliminate apparent immediate hazards to the subjects. A protocol change intended to eliminate an apparent immediate hazard to subjects may be implemented immediately; however, the change must then be documented, reported to the IRB/IEC and Sponsor within 5 working days, who will then submit the deviation to the appropriate regulatory agency in the required time frame, if appropriate.

### **13.2. Financial Disclosure**

Investigators and sub-investigators will provide the Sponsor with sufficient, accurate financial information, as requested by the Sponsor, in order to submit complete and accurate financial certification or disclosure statements to the appropriate regulatory authorities. Investigators are responsible for providing updated information on financial interests periodically, as appropriate.

### **13.3. Subject Information and Consent**

The ICF to be submitted to the IRB/IEC must be reviewed and approved by the Sponsor prior to IRB/IEC submission. Once approved, only the IRB/IEC-reviewed and -approved consent form may be used to consent subjects. The investigator will provide the Sponsor with a copy of the IRB/IEC's written approval as well as the IRB/IEC-approved ICF prior to the start of the study.

At Screening, and at any other time as may be required by the study, subjects/parents/guardians will be presented with the IRB/IEC-approved consent forms and any privacy authorization as required by local and national regulations (such as the Health Insurance Portability and Accountability Act [HIPAA] authorization form). Subjects/parents/guardians will be given a description of the study providing content as per the essential elements of informed consent,

allowed time to ask questions, asked to read the consent form(s) and then provided an opportunity to discuss the contents of these forms with study site personnel.

As the subjects in this study are all minors at study enrollment, parents/guardians will be asked to sign these forms in compliance with ICH GCP and all applicable national and international regulations, before participating in any study-related procedures. Subjects and/or parent/guardian will be made aware that they may withdraw from the study at any time. Subjects unable to give written informed consent must orally assent to the procedures when having reached the appropriate age per local policies and written informed consent must be obtained in accordance with national and local laws, as applicable. Subjects who reach the age of majority (usually 18 years of age) during their participation in the study will be re-consented.

The ICF must contain all applicable elements of informed consent and the mandatory statements as defined by national and local regulations, including confidentiality. All versions of each subject's signed ICF (originals) will be maintained by the site. Copies of the signed copies of the consent form(s) and the HIPAA authorization form, if applicable, will be given to the subject/parents/guardians.

If a subject withdraws consent and/or HIPAA authorization, the investigator may no longer disclose health information, unless it is needed to preserve the scientific integrity of the study.

